#### Calcium and Phosphate Regulation

Serum calcium and phosphate levels are regulated principally by parathyroid hormone (PTH), the active vitamin D metabolite 1,25-dihydroxyvitamin D (1,25[OH]2 vitamin D; calcitriol), and calcitonin. PTH maintains an inverse relationship with serum calcium. Normal total serum calcium levels (generally 8.4 to 10.2 mg/dL) and serum phosphate levels (2.5 to 4.5 mg/dL) are regulated to yield a calcium phosphate product of approximately 35 mg/dL. This product is important because of the potential for calcium phosphate salts to be deposited in soft tissues. Levels of the calcium phosphate product that exceed 50 mg/dL are believed to place patients at risk for ectopic soft tissue calcification. PTH is synthesized and secreted by the parathyroid glands primarily in response to a fall in serum calcium levels. Through concerted actions on the kidney and bone, PTH is the principal regulator of plasma calcium homeostasis. In the kidney,

PTH increases renal tubular reabsorption of calcium (while inversely inhibiting phosphate reabsorption) and increases the synthesis of 1,25(OH)2 vitamin D from its precursor 25-hydroxyvitamin D (25[OH] vitamin D). Although 1,25(OH)2 vitamin D has a short in vivo half-life (approximately 6 hours), it directly increases intestinal calcium and phosphate absorption. In bone, PTH increases the efflux of calcium from bone, both from the rapidly exchangeable pool of calcium within bone, and by increasing the number and activity of osteoblasts and osteoclasts, thereby increasing bone turnover. As PTH also acts to inhibit the reabsorption of phosphate in the proximal nephron, it prevents an increase in plasma phosphate levels that could result from increased intestinal phosphate absorption and efflux of phosphate from bone. Calcitonin, secreted by C-cells of the thyroid gland, decreases serum calcium by inhibiting bone resorption and promoting renal tubular calcium excretion, but its effects are relatively minor in comparison to those of PTH and 1,25(OH)2 vitamin D ([Bilezikian et al. 2001](#)).

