### **Hypoparathyroidism and Hypocalcemia**

The most common cause of chronic hypocalcemia is hypoparathyroidism, a condition in which there is deficient production of PTH from the parathyroid glands. Hypoparathyroidism results in decreased calcium reabsorption from renal tubules, malabsorption of calcium from the GI tract and reduced calcium mobilization from bone. Hypoparathyroidism may result from permanent injury to the parathyroid gland(s) during thyroid or parathyroid surgery or other surgical procedures in the neck, radiation to the neck region, autoimmune destruction of the parathyroid glands, or their congenital absence. Although rare, hypoparathyroidism can also result from genetic mutations, such as activating mutations in the calcium-sensing receptor (CaSR) gene that encodes CaSRs present on parathyroid and kidney tubule cells. Activating mutations of the CaSR gene result in an inappropriately low PTH secretion for the prevailing serum calcium level and increased fractional clearance of calcium by the kidney.

Since free ionized serum calcium stabilizes neural and muscle cell membranes, hypocalcemia can lead to neuromuscular irritability and contribute to the chief signs and symptoms of hypoparathyroidism, which are tetany, twitching, paresthesia, tremor, and spasm. Seizures and laryngospasm are severe symptomatic manifestations. Hypocalcemia may also influence cardiac function by inducing arrhythmias, hypotension, or heart failure. Psychiatric symptoms (anxiety,

irritability, depression, or delirium) may also be present in patients with hypocalcemia. Latent tetany may be demonstrated by eliciting a positive Chvostek sign (hyperirritability of the facial nerve when tapped) or Trousseau sign (carpal spasm induced by brachial nerve ischemia produced by inflating an arm blood pressure cuff above systolic for about 3 minutes). The manifestations of hypocalcemia, when present, vary greatly in severity among patients with hypoparathyroidism.

In hypoparathyroidism, concomitant hyperphosphatemia is a frequent occurrence. A resulting high calcium phosphate product may lead to the deposition of calcium phosphate salts in soft tissues. Such soft tissue calcification can result in important morbidities that include renal parenchymal damage and premature cataracts. Imaging studies in patients with hypoparathyroidism may reveal calcification of the basal ganglia and the grey-white matter interface in the brain.

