### 2.3.3 Other Efficacy Endpoints

- Mean percentage changes from baseline in supplemental oral calcium and supplemental calcitriol dosages at each visit
- Proportion of subjects achieving the first three conditions of the efficacy endpoints defined above, at each visit
- Mean change from baseline in 24-hour urine calcium excretion
- Impact of calcium source (carbonate vs. citrate) on response
- Impact of calcium-sparing diuretics on serum and urinary calcium
- Proportion of subjects that maintain a calcium phosphate product  $\leq 55 \text{ mg}^2/\text{dL}^2$  ( $4.4 \text{ mmol}^2/\text{L}^2$ )
- Distribution of subjects by rhPTH[1-84] doses at the End of Treatment Visit
- Change from baseline in bone turnover markers (bone-specific alkaline phosphatase [BSAP], serum procollagen type 1 amino-terminal propeptide [P1NP], serum carboxy-terminal telopeptide of type I collagen [s-CTX], and osteocalcin), PTH antibodies, and BMD by DXA
- Additional subgroup analyses that are specified in the Statistical Analysis Plan (SAP)

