### 3 STUDY DESIGN

#### 3.1 Overall Design and Control Methods

This study is a long-term, open-label study using rhPTH[1-84] for the treatment of adult male and female subjects with hypoparathyroidism. The subjects must have previously completed the NPSP558 RELAY study (8 weeks of active therapy) and/or previously completed the NPSP558 REPLACE study (CL1-11-040) (Visit 18).

The goal of this study is to optimize rhPTH[1-84] dosing while reducing calcitriol and oral calcium (carbonate or citrate) supplementation to as low as safely possible while maintaining total serum calcium levels (see [Appendix 2](#), rhPTH[1-84] and Supplement Titration Guideline).

- The starting dose of rhPTH[1-84] for this study will be 25 or 50 µg SC once daily (QD).
- Subjects with a total serum calcium value of  $\leq 9.5$  mg/dL will have a starting dose of 50 µg.
- Subjects with a total serum calcium value of  $> 9.5$  mg/dL will have a starting dose as follows:
  - Subjects who are taking supplements ( $\geq 500$  mg calcium and/or any calcitriol) will have the supplements reduced or stopped and will start at a dose of 50 µg SC QD.
  - Subjects who are taking minimal or no supplemental calcium ( $< 500$  mg) and no calcitriol will have a starting dose of 25 µg SC QD.
- Study visits during the first 12 months of the study will be conducted at Weeks 1 (baseline), 4, 8, and then every 8 weeks thereafter up to Week 48 (Visit 8). The Week 52 visit (Visit 9) is scheduled 4 weeks later.
- At the end of Week 52, subjects will be invited to extend their study drug regimen until January 2018 or after the completion of the last patient's Month 72 visit, whichever comes last. During this time, subjects will return to the clinic for interim visits every 2 months (Months 14, 16, 18, etc).
- All subjects will have their total serum calcium checked by a local laboratory 3 to 5 days ( $\pm 2$  days) following the baseline visit.
- Subjects may have their rhPTH[1-84] dose increased in increments of 25 µg to a maximum of 100 µg SC QD by the investigator at any time during the study, with the goal of achieving or maintaining total serum calcium levels in the range of 8.0 to 9.0 mg/dL. The rhPTH[1-84] dose may be adjusted downward at any time as needed to maintain appropriate serum calcium levels (approximately 8.0 to 9.0 mg/dL) or due to any safety concerns.

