3.4.2. Changes from Analyses Planned in the Protocol

No changes from protocol specified analyses are planned.

4. Efficacy and Safety Variables

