4.3. Other Efficacy Endpoints

- Mean percentage changes from baseline in supplemental oral calcium and supplemental calcitriol dosages at each visit
- Proportion of subjects achieving the three conditions of the efficacy endpoint defined above at each visit
- Mean change from baseline in 24-hour urine calcium excretion
- Impact of calcium source (carbonate vs. citrate) on response
- Impact of calcium-sparing diuretics on serum and urinary calcium
- Proportion of subjects that maintain a calcium phosphate product in the range of 35 to 55 mg^2/dL^2
- Distribution of subjects by rhPTH[1-84] doses at the End of Treatment Visit
- Change from baseline in bone turnover markers, bone-specific alkaline phosphatase, serum carboxy-terminal telopeptide of type I collagen, serum procollagen type I amino-terminal propeptide, osteocalcin, PTH antibodies, and BMD by DXA
- Additional subgroup analyses that are specified in the SAP

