6.7.2. Other Analyses

Mean percentage changes from baseline in supplemental oral calcium and supplemental calcitriol dosage at each visit

The absolute and percentage changes from baseline will be summarized at each visit. No formal statistical test will be done.

Proportion of subjects achieving the primary endpoint at each visit

The number and percentage of subjects achieving the primary efficacy endpoint will be presented by visit. No formal statistical test will be done.

Mean percentage change from baseline in 24-hour urine calcium excretion

The absolute and percentage changes from baseline will be summarized by visit. No formal statistical test will be done.

Impact of calcium source (carbonate vs. citrate) on response

The number and percentage of subjects meeting the criteria of being responders will be presented by visit and by calcium source (carbonate vs. citrate). No formal statistical test will be done.

Impact of calcium-sparing diuretics on serum and urinary calcium

The number and percentage of subjects who use at least one calcium-sparing diuretics during the study will be presented.

The urinary calcium will be listed for subjects who received calcium-sparing diuretics during the study. No formal statistical test will be done.

Proportion of subjects that maintain a calcium phosphate product in the range of 35 to 55 mg²/dL²

Calcium phosphate product will be classified as normal (35 - 55 mg²/dL²), or abnormal (including low and high). The number and percentage of subjects with maintenance of a calcium phosphate product in the normal range will be presented by visit. No formal statistical test will be done.

Distribution of subjects by rhPTH[1-84] doses at the End of Treatment Visit

The number and percentage of subjects at different dose levels at the EOT visit will be summarized. No formal statistical test will be done.

Change from baseline in bone turnover markers (bone-specific alkaline phosphatase, serum carboxy-terminal telopeptide of type I collagen, serum procollagen type I amino-terminal propeptide, and osteocalcin), PTH and ECP antibodies, and BMD by DXA

The absolute and percentage changes from baseline will be summarized by visit. No formal statistical test will be done. For DEXA, Z-scores will also be presented and summarized.

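### The calcium-phosphate product endpoint has two current definitions (≤55 and 35–55 mg²/dL²), and the SAP's unexplained floor at 35 scores much of the normal phosphate range as abnormal at target calcium

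*SAP*

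**What the plan says.** The endpoint appears in five places, in two forms.

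- **Protocol 2.3.3 and 8.3:** "Proportion of subjects that maintain a calcium phosphate product" of at most 55 mg²/dL² (4.4 mmol²/L²). No lower limit is given.
- **Protocol synopsis, Other Efficacy Endpoints:** a range of 35 to 55 mg²/dL², followed by the single SI figure 4.4 mmol²/L².
- **SAP 4.3:** "Proportion of subjects that maintain a calcium phosphate product in the range of 35 to 55" mg²/dL².
- **SAP 6.7.2:** "Calcium phosphate product will be classified as normal (35 - 55 mg²/dL²), or abnormal (including low and high"). The number and percentage in the normal class are then shown by visit, without a test.

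On departures from the protocol, SAP 3.4.2 says "No changes from protocol specified analyses are planned".

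Three other statements bear on the choice of limits. Protocol 1.1 (Calcium and Phosphate Regulation) gives "Normal total serum calcium levels (generally 8.4 to 10.2 mg/dL) and serum phosphate levels (2.5 to 4.5 mg/dL") and says that these "are regulated to yield a calcium phosphate product of approximately 35" mg²/dL². The same paragraph links a product above 50 to soft-tissue calcification and names no risk for a low product. Protocol 3.1 has the dose adjusted "with the goal of achieving or maintaining total serum calcium levels in the range of 8.0 to 9.0 mg/dL".

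**The concern.** Two programmers working from current text could report different proportions for the same endpoint, and SAP 3.4.2 would tell neither of them that a choice had been made.

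The choice matters because the floor lies inside the normal range. Protocol 1.1 offers 35 as a typical product, not as a lower bound of health. The trial holds calcium at 8.0–9.0 mg/dL, which is low in, or just below, the quoted normal range, so products at normal phosphate are pulled further down. The disease problem that the protocol describes is on the other side: "In hypoparathyroidism, concomitant hyperphosphatemia is a frequent occurrence", with a high product as the consequence.

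Under SAP 6.7.2 a subject whose phosphate comes down from raised to mid-normal at target calcium can therefore change from normal to abnormal. Low and high share one class, so a reader who sees the normal proportion fall cannot tell whether products have risen above 55 or dropped below 35.

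**Working it through.** **Inputs.** Calcium target 8.0–9.0 mg/dL (Protocol 3.1). Normal calcium 8.4–10.2 and normal phosphate 2.5–4.5 mg/dL (Protocol 1.1). Limits 35 and 55 mg²/dL² (SAP 6.7.2). The distribution of phosphate on treatment is not given, so every percentage below rests on an assumed one.

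**1. The plan's own conversion.** With 1 mmol/L equal to 4.008 mg/dL for calcium and 3.097 mg/dL for phosphate (as phosphorus), 55 / (4.008 × 3.097) = 4.43, which agrees with the stated 4.4 mmol²/L². The lower limit would convert to 35 / (4.008 × 3.097) = 2.82, and no document gives that figure. The synopsis states a two-sided range but an SI value for its upper end only.

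**2. Where 35 sits.** Product = calcium × phosphate.

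| Region | Lowest | Midpoint | Highest |
|---|---|---|---|
| Normal calcium, normal phosphate | 8.4 × 2.5 = 21.0 | 9.3 × 3.5 = 32.6 | 10.2 × 4.5 = 45.9 |
| Target calcium, normal phosphate | 8.0 × 2.5 = 20.0 | 8.5 × 3.5 = 29.75 | 9.0 × 4.5 = 40.5 |

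Both midpoints are below 35.

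**3. Phosphate needed to be scored normal.** The limits are 35/calcium and 55/calcium. The last column is the share of the interval 2.5–4.5 that lies below 35/calcium, that is (35/calcium − 2.5) / 2.

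| Calcium (mg/dL) | Phosphate for 35 | Phosphate for 55 | Share of 2.5–4.5 below 35 |
|---|---|---|---|
| 8.0 | 4.375 | 6.875 | 94% |
| 8.5 | 4.12 | 6.47 | 81% |
| 9.0 | 3.89 | 6.11 | 69% |

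**4. Base case: uniform calcium 8.0–9.0 and uniform phosphate 2.5–4.5.** The mean of 35/calcium over 8.0–9.0 is 35 × ln(9/8) = 4.122. The share below 35 is (4.122 − 2.5) / 2 = 0.811, or 81%. Over the full normal calcium range, 35 × ln(10.2/8.4) / 1.8 = 3.775 and (3.775 − 2.5) / 2 = 0.638, or 64%.

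**5. Other assumed phosphate shapes** (simulation, calcium uniform 8.0–9.0, phosphate kept within normal; SD 0.4 and 0.6 for the truncated normals).

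| Phosphate distribution | Scored below 35 |
|---|---|
| Truncated normal, mean 3.5 | 88–93% |
| Truncated normal, mean 4.0 | 69–72% |
| Truncated normal, mean 4.2 | 55–65% |
| Truncated normal, mean 4.5 | 37–54% |
| Uniform 3.9–4.5 | 37% |
| Uniform 4.0–4.5 | 27% |

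More extreme shapes go further both ways: about 10% for uniform 4.2–4.5, and 96% or more for a truncated normal with mean 3.0.

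**6. One subject.** At calcium 8.5, phosphate 5.5 gives 46.75 (normal under the SAP). Phosphate 3.5 gives 29.75 (abnormal). Under ≤55 both pass.

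**7. Effect of the protocol-body rule.** The largest product in the target-calcium, normal-phosphate region is 40.5, so all of it passes, against about 19% in the uniform base case under 35–55.

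**The case against.** The strongest reply is that little hangs on this row. It is one of the other efficacy endpoints, shown as counts and percentages with no test, in a study whose primary objective is long-term safety and tolerability. SAP 6.8.2 separately summarises serum chemistry by visit with change from baseline and low/normal/high shift tables, and it flags phosphate of 2 mmol/L or more (2 × 3.097 = 6.19 mg/dL). A reader could see phosphate normalising there. This stands, and it limits the severity.

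It is also fair to say that the SAP did not invent the range. The current synopsis has it, so the protocol contradicts itself and the SAP follows one of its two versions. A reader might infer from SAP 3.4.2 an undisclosed departure by the SAP alone, and the documents do not support that.

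Three further inferences are tempting and go too far.

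- **That most subjects will be scored abnormal.** The 81% is a share of a rectangle, not of subjects. In a population described as often hyperphosphatemic, phosphate may cluster at the top of normal or above it, and the share then drops.
- **That the floor lets raised phosphate pass.** At any calcium from 8.0 to 9.0 mg/dL, phosphate above 4.5 and up to about 6.1 mg/dL passes under either rule, because the upper limit decides that.
- **That the endpoint runs backwards overall.** A subject who falls from above 55 into 35–55 improves under both rules. The net direction depends on baseline products, which are not given, and the summary in Protocol 1.2 calls the effect on renal phosphate handling only potential.

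Finally, the two-sided range may be deliberate, since it appears in three places. No rationale is given in any of them.

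**Conclusion.** The point holds as an unresolved conflict of definition with an unsupported lower limit. It is established from the text alone that the protocol body and the synopsis/SAP define the endpoint differently, that SAP 3.4.2 does not acknowledge this, and that 35 lies inside the product range implied by the protocol's own normal values. By arithmetic alone, at target calcium any phosphate below 3.89 mg/dL is scored abnormal, and at the low end of target so is any below 4.375.

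How many subjects this affects is not established. The 81% assumes uniform values, and 27% to 93% is a reasonable span across the other shapes tried. What does not depend on the distribution is that the floor can turn a move from raised to mid-normal phosphate into a change from normal to abnormal, and that the pooled class conceals the reason. The consequence is a by-visit proportion that can mislead. No test or primary conclusion is affected. It should be fixed before the final tables are produced.

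**What to change.** Bring the synopsis, SAP 4.3 and SAP 6.7.2 into line with Protocol 2.3.3 and 8.3: report by visit the proportion of subjects with a product of at most 55 mg²/dL² (4.4 mmol²/L²). Replace the single abnormal class with two separate descriptive rows, <35 and >55, so that the direction of any change is visible.

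If 35–55 is what the sponsor intends, give the reason for the lower limit, correct Protocol 2.3.3 and 8.3, and record the difference in SAP 3.4.2. The separate rows are still worth having in that case.

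The cost is a few lines of wording, a recode of one derived variable and one extra table row. No new data are needed.

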3.1. General Description

This study is a long-term, open-label study using rhPTH[1-84] for the treatment of adults with hypoparathyroidism. Subjects can enroll if they either previously completed the NPSP558 RELAY study (PAR-C10-007) (8 weeks of active therapy) and/or completed the REPLACE study (CL1-11-040) (Visit 18).

The goal of this study is to optimize rhPTH[1-84] dosing while reducing calcitriol and oral calcium (carbonate or citrate) supplementation to as low as safely possible and maintaining total serum calcium levels. Dose adjustments to rhPTH[1-84] and to the calcium/calcitriol supplements and safety monitoring of calcium levels are explained in protocol Appendix 2, rhPTH[1-84] and Supplement Titration Guideline.

- The starting dose of rhPTH[1-84] for this study will be 25 or 50 µg SC once daily (QD)
- Subjects may have their rhPTH[1-84] dose adjusted by the investigator at any time during the study, with the goal of achieving or maintaining total serum calcium levels in the range of 8.0 to 9.0 mg/dL.
- If **ANY** predose (trough) total serum calcium is >11.9 mg/dL study drug will be stopped.
- Subjects will have blood draws to assess total serum calcium levels (which may be performed locally) 3 to 5 days after **ANY** dose adjustment of rhPTH[1-84], after any significant change in doses of calcium and/or calcitriol supplements, or at any other time at the discretion of the investigator.
- Study visits during the first 12 months of the study will be conducted at Weeks 1 (baseline), 4, 8, and then every 8 weeks thereafter up to Week 48 (Visit 8). The Week 52 visit (Visit 9) is scheduled 4 weeks later.
- At any time following the Week 16 (Visit 4), subjects who are on a stable dose of rhPTH[1-84] and have a 24-hour urine calcium >300 mg (males) and >250 mg (females) may be treated for hypercalciuria with calcium-sparing diuretics, if this therapy had not been introduced prior to the study.
- At the end of Week 52, subjects will be invited to extend their study drug regimen until January 2018 or after the completion of the last patient's Month 72 visit, whichever comes last..
- During this time, subjects will return to the clinic for interim visits every 2 months (Months 14, 16, 18, etc).

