6.7. Analysis of Efficacy

All efficacy analyses will be conducted on the ITT Population.

Prescriptive analyses will be presented by visit in order to see how the status or value changes over time. The EOT status or value will be included as a separate time point in the summary.

Efficacy endpoints based on the calcium and/or calcitriol supplement will be derived using both the investigator prescribed data and subject diary data. Computation of daily calcium and calcitriol dose is specified in Section 7.4.1. Analysis based on the investigator prescribed data will be primary. Analysis based on the subject diary data will be considered as supportive.

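### The calcium phosphate product endpoint is named as subjects who maintain a range, but the SAP reports only the percentage in range at each visit, which does not estimate how many stay in range over time

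*SAP*

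**What the plan says.** SAP 4.3 lists the endpoint as "Proportion of subjects that maintain a calcium phosphate product in the range of 35 to 55" mg²/dL². Protocol 2.3.3 begins it the same way, "Proportion of subjects that maintain a calcium phosphate product", but then sets only an upper bound of 55, as does Protocol 8.3. The Protocol synopsis has 35 to 55, like the SAP.

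For the analysis, SAP 6.7.2 labels a product of 35 to 55 normal and any other value abnormal, whether low or high. It then says: "The number and percentage of subjects with maintenance of a calcium phosphate product in the normal range will be presented by visit". This follows the general rule in SAP 6.7: "Prescriptive analyses will be presented by visit in order to see how the status or value changes over time". End of treatment is one more cross-section: "The EOT status or value will be included as a separate time point in the summary". SAP 5.1 defines it as the last available on-treatment value.

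No rule links one visit to another: there is no all-visits criterion, no minimum share of visits and no time to first value out of range. SAP 6.7.4 and 6.7.5 plan no exploratory or sensitivity analysis. Under SAP 6.8.2, individual laboratory values appear in listings.

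**The concern.** Staying in range is a property of one subject followed over time. Being in range at a given visit is a property of the group on that occasion. The planned table gives the second under the name of the first. If the same few subjects are out of range at every visit, the by-visit percentage is close to the proportion who stay in range. If different subjects drift out at different visits, it can be far above it. The table cannot distinguish the two situations.

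What is at stake is the interpretation of one line in the report. Protocol 1.1 gives the product its importance through soft-tissue deposition in individual patients, and the study is about long-term treatment. A per-subject summary is therefore the more informative one, and the data for it are already collected.

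**Working it through.** **No figure to reproduce.** The documents give no target, expected rate or within-subject correlation for this endpoint. The sample size of about 50 is not based on statistical assumptions (SAP 3.3). The following shows only what the planned table can and cannot reveal.

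**Inputs from the documents.**
- Post-baseline visits in Year 1 (SAP 3.1): Weeks 4, 8, 16, 24, 32, 40, 48 and 52, so 8.
- Extension visits every 2 months from Month 14: (36 − 14)/2 + 1 = 12 to Month 36, and (72 − 14)/2 + 1 = 30 to Month 72.
- Cumulative number of visits k: 8 at Week 52, 20 at Month 36, 38 at Month 72.
- Calcium and phosphate are measured at each of these visits (Protocol 6.2.3), so the product is available each time.

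**Assumptions.** The same in-range rate p = 0.90 at every visit, full attendance, and, for this calculation, maintaining read as in range at every visit. None of these is in the documents.

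**Step 1: bounds without a model.** The share always in range lies between max(0, 1 − k(1 − p)) and p.
- k = 8: 1 − 8 × 0.10 = 0.20, so 20% to 90%.
- k = 20: 1 − 20 × 0.10 < 0, so 0% to 90%.
- k = 38: 1 − 38 × 0.10 < 0, so 0% to 90%.

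**Step 2: latent normal model.** With a subject effect U ~ N(0,1) and latent correlation r, the share always in range is E[Φ((z + √r·U)/√(1 − r))^k], where z = Φ⁻¹(0.90) = 1.28. At r = 0 this is 0.90^k.

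| Latent r | Implied correlation of in-range status | Week 52, k = 8 | Month 36, k = 20 | Month 72, k = 38 |
|---|---|---|---|---|
| 0 | 0 | 43% | 12% | 1.8% |
| 0.3 | 0.13 | 56% | 35% | 23% |
| 0.5 | 0.25 | 63% | 48% | 39% |
| 0.7 | 0.41 | 71% | 62% | 55% |

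With p = 0.95, the Month 72 column becomes 14%, 42%, 57% and 71%.

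**Step 3: a second model.** A beta-binomial puts the correlation directly on in-range status. At p = 0.90 and correlations 0.1, 0.3 and 0.5 it gives 54%, 67% and 76% at Week 52, and 21%, 48% and 65% at Month 72. The correlation scale differs from Step 2, so the two sets do not conflict.

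**Step 4: a less strict rule.** Suppose a subject needs at least 90% of 38 values in range, which is 35 or more (0.9 × 38 = 34.2). In the Step 2 model at p = 0.90, 47% of subjects qualify at r = 0 and 62% to 75% at r = 0.3 to 0.7. Two consecutive values out of range, in either direction, occur in 29% of subjects at r = 0, falling to 21% at r = 0.7. The by-visit table shows neither quantity.

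**The case against.** The strongest reply is that the documents use the word for a status at one time. In SAP 4.2 and 6.7.1, serum calcium is judged normalized or maintained against baseline at Week 52 and/or end of treatment, with no history required. By-visit display is the SAP's general design. This stands as an account of what was probably intended. It means the label is loose, and that the all-visits reading is only one option. The sentence could also be read as cumulative maintenance up to each visit, but no such rule is written.

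Three stronger readings are tempting, and the documents do not support them.

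- *Most subjects will not have maintained the range.* This needs an all-visits definition, an assumed rate, full attendance, many visits and low to moderate correlation. At 90% per visit and r = 0.7, 55% are still always in range at Month 72. At Week 52 the share is 56% to 71% for r = 0.3 to 0.7.
- *The planned figure overstates control of a high product.* The SAP counts values below 35 as abnormal. Protocol 1.1 puts normal phosphate at 2.5 to 4.5 mg/dL. With the study's calcium target of 8.0 to 9.0 mg/dL, the product runs from 8.0 × 2.5 = 20 to 9.0 × 4.5 = 40.5, much of it below 35. The percentage could therefore understate freedom from high values.
- *Calcification depends on sustained elevation.* Protocol 1.1 links a high product to risk but does not say that the elevation must be repeated or prolonged.

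There is also partial cover elsewhere. SAP 6.8.2 counts subjects with markedly abnormal post-baseline phosphate (2 mmol/L or more) or calcium (3.0 mmol/L or more). These are per-subject counts, but of the components and not the product.

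Finally, a criterion requiring every value in range favours subjects who leave early, because they have fewer chances to fail. Protocol 4.4 allows exit to commercial drug. That objection is right, and the fix below allows for it.

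**Conclusion.** The point holds as a mismatch between the endpoint's name and its analysis. No planned summary estimates how many subjects keep the product in range over time, and the by-visit percentages cannot be converted into one without the within-subject correlation, which the planned tables do not show.

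The bounds in Step 1 need no model, only the visit count, the assumed 90% rate and full attendance. The narrower figures in Steps 2 to 4 also depend on assumed correlations. They illustrate the range of possibilities and do not forecast the result or the direction of any bias.

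The consequence is minor. This is one of several descriptive endpoints listed as other efficacy, in an open-label study with a safety objective and no formal testing, and no decision rule uses it.

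**What to change.** Amend SAP 4.3 and 6.7.2 as follows.

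1. Relabel the existing table as in range at visit and keep it as supportive.
2. Add a per-subject summary of the share of each subject's on-treatment values within the limit: median, quartiles, and the percentage of subjects with at least 90% of values within it.
3. Report the percentage of subjects with two consecutive values above the upper limit.
4. Show low and high values separately, so that a low product is not mixed with a high one.
5. Present these by length of follow-up or over fixed periods (for example to Week 52 and to Month 36 among subjects with data), with a stated minimum number of values and a rule for missed visits, so that early leavers do not look better.
6. In the same edit, reconcile the range of 35 to 55 (Protocol synopsis, SAP 4.3 and 6.7.2) with the upper bound of 55 alone (Protocol 2.3.3 and 8.3), since the choice changes who counts.

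The cost is SAP wording and one extra table from data already collected. The reported maintenance figure may be less favourable than the by-visit percentages.
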